1 PROTOCOL SUMMARY

1.1 SYNOPSIS

Title:	Preventing medication dispensing errors in pharmacy practice with interpretable machine intelligence – Images Wave 3	
Study Description:	This study is the third wave of the participatory design process and a formative evaluation to refine the human-machine intelligence (MI) collaboration for the pharmacy verification task in a simulated environment.	
Objectives:	Primary Objectives:	Determine the impact of MI assistance on task time, error detection rate, and users' trust
	Secondary Objectives:	Examine the effect of MI assistance on cognitive effort
Endpoints:	Primary Endpoints:	Task time, decision accuracy, and trust
	Secondary Endpoints:	Cognitive effort
Study Population:	Licensed pharmacists in the United States with medication dispensing experience who are 18 or older.	
Study Duration:	12 months	
Participant Duration:	1 day	

2 INTRODUCTION

2.1 STUDY RATIONALE

Medication errors are a major public health problem. Preventable medication errors cost the U.S. healthcare system over \$16 billion annually with \$4.2 billion attributable to preventable outpatient medication errors.¹ Medication errors result in 3 million outpatient medical appointments, 1 million emergency department visits, and 125,000 hospital admissions each year.² In addition to the added costs and strain on the healthcare system, medication errors can result in liability claims against pharmacy staff. The two most common reasons for legal action against licensed pharmacy staff is dispensing of the wrong dose or wrong medication which results in an average settlement of nearly \$125,000.³ There is a critical need to provide pharmacy staff with tools to reduce medication errors thereby improving patient safety and reducing costs.

Pharmacists currently perform an independent double-check to identify drug-selection errors before they can reach the patient. However, the use of machine intelligence (MI) to support this cognitive decision-making work by pharmacists does not exist in practice. Instead, pharmacists rely solely on reference images of the medication which they can compare to the prescription vial contents. Previous research has shown that decision support systems can effectively improve healthcare delivery efficiency and accuracy, while preventing adverse drug events.⁴ However, little is known about how MI technologies impact pharmacists' work performance and cognitive demand.

To facilitate the long-term symbiotic relationship between the pharmacists and the MI system, proper trust needs to be established. While trust has been identified as the central factor for effective human-machine teaming,⁵⁻¹⁵ issues arise when humans place unjustified trust in automated technologies do not place enough trust in them.^{7,8,10,12-15} Over trust in automation can lead to complacency^{9,16} and automation bias.^{17,18} For instance, the pharmacists may rely on the MI system to the extent that they blindly accept any recommendation by the system. Under trust can result in pharmacist disuse and potential abandonment of the MI system.¹⁹

Furthermore, little is known about the timing of the MI advice on pharmacists' work performance. For example, showing the MI's advice while the pharmacist is performing the medication verification task may yield different results than showing the MI's advice after the pharmacist made their decision.

The study investigators have developed a MI system for medication images classification. The objective of this study is to examine the effectiveness of the timing of MI advice to determine if it results in lower task time, increased accuracy, and increased trust in the MI. The objectives of this study are to: 1) evaluate changes in participants' trust due to the use of interpretable machine intelligence; and 2) determine the effect of interpretable machine intelligence on participants' performance in a simulated environment.

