4 STUDY DESIGN

4.1 OVERALL DESIGN

This study will examine the effectiveness of MI assistance on the medication verification process in a mock setting. Pharmacists with medication dispensing experience will be recruited to perform mock verification tasks on a web application on the computer. Webcam-based eye-tracking software will be used to detect eye gaze patterns during verification tasks (<https://www.labvanced.com/>).

Participants will attend one 3-hour remote visit. During this visit, participants will complete a series of 300 remote verification tasks. Prior to starting the verification tasks, participants will complete 3 surveys: 1) a demographics survey 2) the propensity to trust scale²⁰ and 3) the Occupational Fatigue Exhaustion Recovery Scale.²¹ Each participant will then receive a 15-minute self-guided training session that introduces the study and teaches participants how to use the interface and perform the medication verification task. In each verification task, participants will compare the image on the left (i.e., the medication filled for a prescription) to the image on the right (i.e., a known reference image) and decide whether to accept or reject the images as containing the same prescribed medication.

Pharmacists will be presented with 3 conditions: No help group, Scenario #1, and Scenario #2 (see Figure 1). The order of the conditions will be randomized. In the No help group, participants will complete the verification task without any artificial intelligence (AI) help. In Scenario #1, participants will receive AI in the form of a pop-up message if their decision differs from the AI's determination. In Scenario #2, AI help will be displayed concurrently with the filled and reference images.

After each verification task in Scenario #1 and Scenario #2, the participants will be asked to respond to a visual analog trust scale (e.g., How much do you trust the automation with the left anchor "I completely distrust the MI" and the right anchor "I completely trust the MI"?).^{20,22} After each condition, participants will complete 2 brief surveys - System Usability Scale,²³ NASA Task Load Index.²⁴ After Scenario #1 and Scenario #2, participants will also complete a trust scale.²⁵

To approximate a real-world experience in this mock setting, 20% of images provided in these verification tasks for each participant will differ from labels in prescriptions (i.e., an incorrectly filled prescription).

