Figure 1. Interfaces for each study condition evaluating the effect of machine intelligence (MI) on work performance and pharmacist trust. Top: No MI help; Middle: MI help; Bottom: AI help when disagreement between user and AI

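### Section 2.1 sets the timing of MI advice as the objective, but Scenario #1 and Scenario #2 also differ in display rule, so their contrast cannot isolate timing

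*Combined protocol and SAP*

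**What the plan says.** The rationale (section 2.1) motivates the study with a timing question: "showing the MI's advice while the pharmacist is performing the medication verification task may yield different results than showing the MI's advice after the pharmacist" has decided. It then gives the objective as to "examine the effectiveness of the timing of MI advice to determine if it results in lower task time", adding accuracy and trust. Neither sentence makes the advice conditional on disagreement.

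Section 4.1 defines the conditions: "Pharmacists will be presented with 3 conditions: No help group, Scenario #1, and Scenario #2".

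- **No help:** "In the No help group, participants will complete the verification task without any artificial intelligence (AI) help".
- **Scenario #1:** "participants will receive AI in the form of a pop-up message if their decision differs from the AI's determination".
- **Scenario #2:** "AI help will be displayed concurrently with the filled and reference images".

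The Figure 1 caption draws the same distinction between the two advice interfaces: "Middle: MI help; Bottom: AI help when disagreement between user and AI".

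The other sections are more general. Section 3 speaks of the impact of MI assistance. Section 7.1 hypothesises that time and accuracy differ among the three scenarios and that trust differs between Scenario 1 and Scenario 2. Section 7.3.1 tests differences among conditions. None of these names timing.

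**The concern.** A timing objective needs two conditions that differ in when advice appears and in nothing else that could affect the outcome. Here the rule for showing the advice changes together with its timing. In Scenario #1 the visible advice comes after the decision and, by construction, always contradicts the participant. In Scenario #2 it comes during the task and may confirm or contradict.

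Trust is where this matters most. It is a primary endpoint, and its only hypothesis in section 7.1 is Scenario 1 versus Scenario 2. Under section 4.1 the visual analog trust scale is answered after every task in both scenarios, including Scenario #1 tasks on which no message appeared. A trust difference could come from seeing only contradictions, from seeing few messages, or from their timing.

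The synopsis describes a formative evaluation meant to refine how pharmacists and the MI work together. A conclusion that later advice is better or worse could send that refinement in the wrong direction if the display rule produced the effect.

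**Working it through.** **1. Cross the two features.** Advice can be concurrent or post-decision, and it can be shown without an agreement condition or only on disagreement. From section 4.1 and the Figure 1 caption:

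| | No agreement condition | Only on disagreement |
|---|---|---|
| Concurrent | Scenario #2 | not run |
| Post-decision | not run | Scenario #1 |

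The remaining condition, No help, has no advice and so carries no information on either feature. The upper-right cell could hardly exist, because disagreement is not known until the participant has decided.

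**2. Decompose the contrast.** Let M(timing, rule) be the mean outcome in a cell. Then

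Scenario #2 − Scenario #1 = M(concurrent, unconditional) − M(post, disagreement)

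= [M(concurrent, unconditional) − M(post, unconditional)] + [M(post, unconditional) − M(post, disagreement)].

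The first bracket is the timing effect with the display rule held fixed. The second is the display-rule effect with timing held fixed. Both need M(post, unconditional), which is not observed. The study estimates only their sum.

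**3. Could the analysis or the sample size help?** Randomising the order of conditions (sections 4.1 and 6.1) addresses order effects. The ANOVA and mixed models of section 7.3.1 compare conditions. Neither separates the two brackets. The 36 subjects of section 7.2 are given without an effect size, standard deviation, rates or within-subject correlation, so that figure cannot be reproduced. It does not bear on this point, because more subjects would only estimate the same sum more precisely.

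**4. How different could the visible exposure be? Illustration only.** Inputs: 300 tasks in total (section 4.1); an equal split, 300/3 = 100 per condition (assumed); pharmacist accuracy u and AI accuracy m, each 0.85 to 0.99 (assumed); independent errors (assumed). With a two-way accept/reject decision, disagreement means that exactly one of the two is wrong:

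expected pop-ups per 100 tasks = 100 × [u(1 − m) + m(1 − u)].

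- u = m = 0.85: 100 × (0.85 × 0.15 + 0.85 × 0.15) = 25.5
- u = m = 0.90: 100 × (0.90 × 0.10 + 0.90 × 0.10) = 18
- u = m = 0.95: 100 × (0.95 × 0.05 + 0.95 × 0.05) = 9.5
- u = m = 0.99: 100 × (0.99 × 0.01 + 0.99 × 0.01) = 1.98, about 2

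The range is about 2 to 26 tasks per 100. If Scenario #2 shows help on all 100 tasks, which is the natural reading but is not stated, the ratio runs from 100/25.5 ≈ 4 to 100/1.98 ≈ 50. A range this wide gives no usable single figure. Steps 1 to 3 do not depend on it.

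**The case against.** The strongest reply is that timing appears only in the rationale. The sentence after the timing objective restates the aims as trust change and performance under interpretable MI. The synopsis and sections 3, 4.1, 7.1 and 7.3.1 speak only of MI assistance or differences between conditions. This stands, and it limits the point to the claim in section 2.1. It does not remove the point, because that sentence is current text and calls timing the objective of the study.

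Second, a missing pop-up tells a participant who knows the rule that the AI agrees, so Scenario #1 may convey a verdict after every decision. This partly stands. Section 4.1 provides training on the interface but does not say that the rule is explained. What is displayed, how often and on which tasks would still differ.

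Third, a confirmation shown after a decision has little direct route to changing that decision, so the display rule should matter more for trust, workload and usability than for accuracy. This is reasonable, although effects carried from one task to the next are possible. For task time, section 3 stops the clock at acceptance or rejection without saying whether Scenario #1 uses the decision before or after the pop-up.

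A reader might go further and infer that the primary comparisons are invalid, that section 7.1 tests a timing hypothesis, or that exposure differs by some known multiple. The documents support none of these. Comparisons with No help do not rest on separating timing from display rule, section 7.1 makes no timing attribution, and neither an agreement rate nor a task split per condition is given.

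**Conclusion.** The objective sentence in section 2.1 claims more than the design can deliver. Timing and display rule are completely aliased in Scenario #1 versus Scenario #2, the only contrast that could address timing. This follows from the definitions in section 4.1 and needs no assumed number. A difference between the two scenarios in trust, time or accuracy cannot be attributed to timing alone.

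Each scenario versus No help remains interpretable, as does a comparison of the two scenarios as whole packages, and these are what sections 3 and 7.1 describe. The data stay usable; the limit is on the conclusion. The figure of 2 to 26 pop-ups per 100 tasks illustrates how far exposure might differ under the stated assumptions and should not be cited as a finding.

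**What to change.** Reword the objective sentence in section 2.1 so that it compares two delivery modes, for example: 'to compare post-decision advice shown only on disagreement with concurrent advice, in terms of task time, accuracy and trust'. Add one sentence stating that the effect of timing alone is not estimated and will not be concluded from the Scenario #1 versus Scenario #2 contrast.

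The hypotheses in section 7.1 need no correction. No new condition, data or analysis is required. The cost is a small edit and a narrower claim: the study can say which delivery mode did better, but not that timing was the reason.

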3 OBJECTIVES AND ENDPOINTS

OBJECTIVES	ENDPOINTS
Primary	
Determine the impact of MI assistance on task time, decision accuracy rate, trust change and trust.	
 • Difference in task time measured by the number of seconds from starting the task to accepting or rejecting a medication image • Difference in detection rate measured by number of medication verification errors • Difference in trust measured by visual analog trust scale and the trust scale
Secondary	
 • Difference in cognitive effort measured by duration of fixation • Difference in cognitive effort as measured by fixation count • Difference in cognitive effort as measured by dwell time. Dwell time is calculated by summing up the duration of fixations in a region (e.g., the fill image) for each trial. • NASA task load • SUS

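### Trust change is a primary objective, but trust in the MI is first rated after MI use has begun, so change from the level before use cannot be estimated

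*Combined protocol and SAP*

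**What the plan says.** Change in trust is named in two places. Section 2.1 gives the first study objective as to "evaluate changes in participants' trust due to the use of interpretable machine intelligence". Section 3 states the primary objective as "Determine the impact of MI assistance on task time, decision accuracy rate, trust change and trust", listing change and level side by side.

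The matching endpoint in Section 3 is "Difference in trust measured by visual analog trust scale and the trust scale". It gives no change score and no reference time. The synopsis lists trust alone, the hypothesis in Section 7.1 is a difference between Scenario 1 and Scenario 2, and Section 7.3.1 names trust as an outcome without a time term.

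Section 4.1 sets the timing:

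- Before the tasks: "Prior to starting the verification tasks, participants will complete 3 surveys: 1) a demographics survey 2) the propensity to trust scale", the third survey being an occupational fatigue scale.
- During MI use: "After each verification task in Scenario #1 and Scenario #2, the participants will be asked to respond to a visual analog trust scale".
- At the end of a block: "After Scenario #1 and Scenario #2, participants will also complete a trust scale".

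No trust rating is scheduled in the No help condition.

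**The concern.** A change attributed to using a system is most naturally read as a departure from the level held before use. The plan collects no such level for this MI. The propensity to trust scale asks about a general disposition on another instrument. It can serve as a covariate but cannot be subtracted from the VAS.

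Section 2.1 worries about both over-trust and under-trust. Without a starting level, the trial can say which scenario ends with higher trust. It cannot say whether either scenario raised or lowered trust relative to what pharmacists held on arrival. A sharp early move would show in the level but would be partly missing from any change score that starts at the first in-use rating. A rating from before exposure cannot be recovered once the data are collected.

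**Working it through.** The plan has no figure for trust change to reproduce; the 36 subjects in Section 7.2 are justified by detection rates. The check is therefore one of timing.

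**1. Ratings of trust in this MI, by time (Section 4.1)**

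- After training, before any MI task: 0.
- During each MI block: one VAS per task. The split of the 300 tasks is not stated. With an equal split (assumption), 300 / 3 = 100 per block, so 2 × 100 = 200 per participant.
- After each MI block: one trust scale, so 2 per participant.

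**2. What can be estimated.** With 100 ratings per block there are 100 − 1 = 99 task-to-task steps, a first-to-last difference and a slope. Change during use is estimable and can be compared between scenarios. Change from before use has no starting term.

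**3. Whether the first in-block rating can stand in for a baseline**

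- Scenario #2 shows the advice alongside the images, so the first rating already follows advice.
- Scenario #1 shows a pop-up only on disagreement, so the first rating may come before any pop-up.
- In whichever MI block comes second, the first rating follows a full block with the other interface. Three conditions have 3! = 6 orders. If these are balanced over 36 participants (assumption), there are 36 / 6 = 6 per order. Each MI scenario comes after the other in three orders, so this affects 3 × 6 = 18 of 36 participants for each scenario.

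First-to-last change therefore starts from different exposure in the two scenarios and in the two MI periods.

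**4. What a baseline adds to the scenario contrast.** Let b be one rating before exposure, and t1 and t2 the late-block levels in Scenarios #1 and #2. Then (t1 − b) − (t2 − b) = t1 − t2. The baseline cancels. It is needed for the change within each scenario, t1 − b and t2 − b, not for the comparison between them.

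**5. Why the baseline must be single.** Suppose change were instead taken from a rating just before each MI block. For simplicity, assume that in the second MI block this rating equals the level reached at the end of the first. The contrast, change in #1 minus change in #2, is then:

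- Order #1 then #2: (t1 − b) − (t2 − t1) = 2·t1 − t2 − b.
- Order #2 then #1: (t1 − t2) − (t2 − b) = t1 − 2·t2 + b.
- Average over the two orders, which is what a period term delivers: (3·t1 − 3·t2) / 2 = 1.5 × (t1 − t2).

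The first block's effect enters the second block's score, and adjusting for period does not remove it.

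**The case against.** The strongest case against is that the plan already rates trust after every MI task. That schedule fits a reading of trust change as movement during use at least as well as a before-and-after reading, and neither Section 2.1 nor Section 3 says which is meant. The stated hypothesis needs no baseline, since a common one cancels. An early jump would still be seen in trust level, which the same objective names. Participants who meet Scenario #1 before Scenario #2 may give a near-baseline value before any pop-up. The study is formative, and randomized order balances the starting level on average.

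Most of this stands. A reader might infer that trust change cannot be measured at all, or that the comparison of trust between scenarios is compromised. The documents support neither: the VAS series carries within-block change, and the contrast in level is estimable as planned. Nor do they support a figure for how much change is lost by the first rating. If trust moved 5% to 30% of the remaining distance per task, the first rating would miss 5% to 30% of the total and 70% to 95% would remain visible, but that only restates the assumption.

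Two things survive. Change due to use, the wording of the first study objective, has no reference level on either trust instrument. And the near-baseline value in Scenario #1 has no equivalent in Scenario #2, so it does not give a common start.

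**Conclusion.** The point holds in a limited form. Change in trust during MI use can be estimated; change from the level before use cannot, because no rating of trust in this MI precedes the first MI task. The first in-block rating is not a comparable substitute across scenarios or periods. Trust change also lacks an endpoint definition, a hypothesis and a named analysis.

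The size is structural, not numerical: no ratings before exposure against about 200 during it (equal split assumed), and 18 of 36 participants entering each scenario after the other (balanced orders assumed). The documents give no trust data from which to put a bias in VAS units. This is a cheap improvement, not a flaw that undermines the trial.

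**What to change.** - Show the same trust VAS once to every participant, after training and before the first MI task. Straight after training would place it at the same moment in every order.
- Define trust change for each MI scenario as the VAS late in the block (for example the mean of the last ratings) minus this single baseline. Report it per scenario, with the first MI block as the cleanest estimate.
- Compare Scenario #1 with Scenario #2 on VAS level and on within-block trajectory, using a mixed model with scenario, task number, scenario by task number, and period or order. Section 7.3.1 already allows mixed models.
- Do not subtract a rating taken just before a block if the participant has already used the other MI scenario.

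If no baseline is added, define trust change explicitly as within-block change on the VAS, or remove it from the primary objective.

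The cost is one slider click per participant, a small change to the web task and one endpoint definition. The baseline will reflect expectations formed in training. The change from it remains a before-and-after quantity, because trust is not rated in the No help condition. Both limits should be stated when it is reported.

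### Does the plan need to say whether the decision before or after the Scenario #1 pop-up is the one timed and scored?

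*Combined protocol and SAP*

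**What the plan says.** Section 3 gives the primary objective as "Determine the impact of MI assistance on task time, decision accuracy rate, trust change and trust". Its time endpoint is "Difference in task time measured by the number of seconds from starting the task to accepting or rejecting a medication image", and its accuracy endpoint is "Difference in detection rate measured by number of medication verification errors".

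Section 4.1 describes each task as one in which participants "decide whether to accept or reject the images as containing the same prescribed medication". It then sets out when the advice arrives:

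- Scenario #1: "participants will receive AI in the form of a pop-up message if their decision differs from" the system's own classification.
- Scenario #2: "AI help will be displayed concurrently with the filled and reference images".
- No help: no advice at all.

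Section 4.1 also says that "participants will complete a series of 300 remote verification tasks" and that "20% of images provided in these verification tasks for each participant will differ from labels in prescriptions". It refers to Figure 1 for the interfaces. Only the caption can be read here, and it mentions a panel for disagreement between user and AI.

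Sections 7.1 to 7.3.1 (hypotheses, sample size, analysis) add no rule on which decision counts.

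**The concern.** Taken literally, the act that stops the clock in Scenario #1 is the same act that brings up the advice. Time spent reading and answering the pop-up would then fall outside the measured interval, whereas in Scenario #2 time spent on the advice falls inside it. The time comparison between the two advice conditions would be tilted towards Scenario #1 by the disagreement rate multiplied by the mean time spent on a pop-up.

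The accuracy endpoint has a parallel difficulty. If the first decision is scored, a miss that the participant corrects after the pop-up still counts as an error. Within a task, Scenario #1 would then measure unaided performance, and its comparison with No help could show only anticipation or learning.

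Time and accuracy are both primary endpoints, and Section 2.1 names the timing of the advice as what the study is about. A definition left open until the data are in hand could be chosen to suit the result.

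**Working it through.** The plan states no figure for this point. The 36 subjects in Section 7.2 come without an effect size or detection rates, so they cannot be used to tell which decision was meant. The check therefore compares the two readings and then asks how far apart they could be.

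**Which tasks are affected.** No help and Scenario #2 have one decision per task, so nothing is ambiguous there. In Scenario #1, tasks on which participant and AI agree produce no pop-up, so first and final decision coincide. Only Scenario #1 disagreement tasks are open.

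**Two cases on those tasks.**

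1. *The decision can be revised.* A second accept or reject then exists. Section 3 ends the clock at accepting or rejecting and does not say the first such act. If the final act stops the clock, pop-up time is counted in Scenario #1 just as advice time is counted in Scenario #2, and the imbalance disappears.
2. *The decision cannot be revised.* Only one decision exists. Section 3 then defines both time and error without ambiguity, and Scenario #1 results describe decisions made before advice. That is a matter of interpretation.

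**Which reading fits case 1.** The objective asks for the effect of assistance on time and accuracy. Section 4.1 presents the pop-up as the way participants receive the AI in Scenario #1, and places the trust rating after each verification task. Both put the pop-up inside the task, which favours the final decision.

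**Time.** Difference between definitions per Scenario #1 task = disagreement rate × mean pop-up handling time. Both inputs are assumed.

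- 0.02 × 2 s = 0.04 s
- 0.20 × 10 s = 2.0 s
- 0.30 × 10 s = 3.0 s

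The documents give no baseline task time or standard deviation against which to judge these values.

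**Accuracy, one event.** 0.20 × 300 = 60 incorrect fills per participant. If they are split evenly (an assumption), 60/3 = 20 fall in each condition. One corrected miss moves that participant's detection rate by 1/20 = 5 points. Averaged over 36 participants, it moves the condition mean by 5/36 = 0.14 points. The documents give no number of corrections.

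**Accuracy, net effect.** Let p0 be unaided detection of an incorrect fill, s the AI's sensitivity and r the probability of switching after a pop-up, with human and AI errors independent. All are assumptions.

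- First decision: p0
- Final decision: p0[s + (1 - s)(1 - r)] + (1 - p0)sr = p0 + r(s - p0)
- Difference: r(s - p0)

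| p0 | s | r | First | Final | Difference |
|---|---|---|---|---|---|
| 0.70 | 0.95 | 1.0 | 0.70 | 0.95 | +0.25 |
| 0.80 | 0.95 | 0.8 | 0.80 | 0.92 | +0.12 |
| 0.80 | 0.80 | 0.8 | 0.80 | 0.80 | 0.00 |
| 0.90 | 0.80 | 1.0 | 0.90 | 0.80 | -0.10 |

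The sign depends on whether the AI detects incorrect fills better or worse than the unaided pharmacist. A wrong AI determination can also overturn a correct rejection, so counting corrected misses alone would show only one side.

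**The case for a change.** The best argument for a change is that no readable sentence settles the matter, that it touches two primary endpoints, and that one of them, detection rate, is the endpoint named in the sample-size statement. Section 7.1 also calls the time measure reaction time, which leans towards a first response. Disagreement tasks may be a minority, but they are the only ones on which Scenario #1 gives a pop-up. Even a figure showing a second button would not say which press is timed or scored, and one sentence would close the question at almost no cost.

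Much of this stands. The silence is real, and under plausible inputs the two definitions could give different answers.

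It does not show that the plan as written produces a wrong result. The harmful reading requires the analyst to discard the decision made after the advice in a study of what the advice does. The strength of the comparison at risk is also easy to overstate. For time and accuracy, Section 7.1 hypothesises a difference among all three conditions and reserves the two-scenario hypothesis for trust, and Section 7.3.1 ranks none of its 3 pairwise comparisons first. Finally, whether a revision step is missing at all cannot be established while the interface figure is unavailable.

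**Conclusion.** No change to the plan follows. The text leaves an operational definition unwritten for Scenario #1 disagreement tasks, and analysts would fill it sensibly: the final accept or reject if revision is possible, and the only decision if it is not. Under the first rule the timing imbalance vanishes and accuracy includes the pop-up's effect. Under the second, Section 3 is already complete.

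The possible difference between definitions, 0.04 to 3.0 s per task and -10 to +25 points of detection, rests wholly on assumed disagreement rates, handling times, AI sensitivity, unaided detection and switching probabilities. It shows that the definition can matter, and says nothing about the likely effect in this study. The conclusion assumes that the final decision is recorded where revision is allowed, which the documents do not state. In a formative evaluation in a simulated setting, this is a point of clarification and not a demonstrated error.
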